4.7.2 Deaths

Details of any deaths will be presented in the form of an individual patient listing, as well as a frequency table by treatment.

4.7.3 Laboratory Data

All laboratory data will be converted to SI units. The International Standard for the Handling and Reporting of Laboratory Data COG 3007 (Version 4.0) will be used to implement reference ranges and marked abnormalities for laboratory data where possible.

For each of the haematological and biochemical test parameters, summary statistics of observed and change from baseline values at Day 10 will be presented by treatment group. Baseline is defined as the last assessment prior to treatment on Day 1.

A listing will present all lab assessments data for patients who had any significant change from baseline.

Summaries of the number of patients by CTC grade at each assessment will also be presented. For laboratory parameters, observations on Day 1 will be classed as baseline.

Additionally, summary statistics of observed and change from baseline values of liver function tests (Total Bilirubin, Alkaline phosphatase [ALP], Alanine aminotransferase [ALT] and aspartate aminotransferase [AST]), which are collected on Day 1, Day 4, Day 7 (if 3rd dose of baloxavir received) and Day 10, will be presented by treatment group for each scheduled time point, as well as box and whisker plots at each time point.

The number and proportion of patients who meet the pre-specified criteria shown in [Table 14](#) will be presented by treatment group during the study.

Table 14 Pre-specified Abnormal Laboratory Criteria

AST (U/L) or ALT (U/L) and Total bilirubin (mg/dL)
AST(U/L) or ALT (U/L) > 3 × ULN
AST(U/L) or ALT (U/L) > 5 × ULN
AST (U/L) or ALT (U/L) > 3 × ULN and Total bilirubin (mg/dL) > 2 × ULN

ALT= Alanine aminotransferase; AST= aspartate aminotransferase; ULN = upper limit of normal.

A listing of all pregnancies will be presented.

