4.5.8 Liver Function Monitoring

Patients should be assessed for liver function prior to each dose of baloxavir marboxil or matching placebo.

On Day 1 and Day 4, the assessment is mandatory. On Day 1, the local laboratory full blood chemistry panel required as part of screening can be used for this assessment or prior blood results if tests conducted within 24 hours prior to screening. On Day 4, the

protocol-required local laboratory blood liver chemistry panel should be used for this assessment.

On Day 7, the local laboratory blood liver chemistry panel and associated review of liver chemistry is only required if the patient will receive baloxavir marboxil or matching placebo on this study day.

Results must be reviewed by the investigator before dose administration. Dosing will occur only if the clinical assessment and local laboratory liver chemistry panel values are acceptable (see [Appendix 4](#)).

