4.4 VISIT WINDOWS

Visit windows will only be applied to scheduled time points for laboratory parameters. This will include full blood hematology and chemistry assessments at Day 1 and Day 10, and blood liver chemistry assessment before dosing with the study treatment on Day 1, Day 4 and Day 7 (if study treatment is planned on Day 7) (Table 2). No other visit windows will be used in the study analysis.

Table 2 Acceptable Time Windows – Laboratory Parameters

Time Point (Scheduled Time Point)	Acceptable Time Window
Visit 1 (Day 1)	pre-dose Day 1
Visit 4 (Day 4)	Between Day 3 and Day 5 as follows: -if patient presents on Day 4 this will be classed as Visit 4; -if patient presents on Day 3 with no Day 4, and no Day 5 this will be classed as Visit 4; -if patient presents on Day 5 with no Day 4, and no Day 3 this will be classed as Visit 4; provided this is the day study treatment was received.
Visit 6 (Day 7)	Between Day 6 and Day 8 as follows: -if patient presents on Day 7 this will be classed as Visit 6; -if patient presents on Day 6 with no Day 7, and no Day 8 this will be classed as Visit 6; -if patient presents on Day 8 with no Day 7, and no Day 6 this will be classed as Visit 6; provided this is the day study treatment was received, per protocol guidance.
Visit 7 (Day 10)	Between Day 8 and Day 12

Measurements collected within the acceptable time window for each scheduled assessment time point, including data obtained at the time of withdrawal, will be used for the analyses at each assessment time point. For all patients with multiple values within a visit window, the value obtained closest to the target time point (Day 1 and Day 10) will be used for the full blood chemistry and haematology evaluations. The value obtained prior to the target time (Day 4 and Day 7) will be used for the pre-study treatment blood liver chemistry. The assessment time point having no measurements within the corresponding acceptable time window will be considered as missing.

For summaries of data not collected by visit, such as adverse events, medical history and concomitant medications, all data up to the end of study will be included.

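### As worded, the SAP's Day 7 and off-day rules for liver samples can leave out of the by-time-point liver displays the pre-dose values that barred a dose

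*SAP*

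**What the plan says.** Protocol 4.5.8 requires liver function to be checked before each dose of baloxavir or placebo: "Results must be reviewed by the investigator before dose administration". Dosing goes ahead only if the panel is acceptable, and Appendix 4 has study medication stopped when one of its liver criteria is met. The Day 7 panel is required only in patients who are to be dosed that day, in either arm.

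The SAP states the Day 7 condition in two ways. The text of 4.4 lists the pre-dose liver assessment for "Day 7 (if study treatment is planned on Day 7". Section 4.7.3, after naming the first two collection days for liver tests, continues "Day 7 (if 3rd dose of baloxavir received) and Day 10, will be presented by treatment group for each scheduled time point", and adds box plots at each time point.

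Table 2 in 4.4 then assigns samples to visits. For Visit 4 the first line is unconditional: "if patient presents on Day 4 this will be classed as Visit 4". Lines for a lone Day 3 sample and a lone Day 5 sample follow, and the last carries the condition "provided this is the day study treatment was received". Visit 6 has the same structure for Days 7, 6 and 8, and ends "provided this is the day study treatment was received, per protocol guidance". If nothing qualifies, "The assessment time point having no measurements within the corresponding acceptable time window will be considered as missing".

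**The concern.** A pre-dose panel decides whether the dose is given. A rule that keeps the panel only when the dose was received therefore selects on the value being measured: acceptable results stay and results that barred the dose go. The by-time-point means, changes from baseline and box plots would be cut at the upper end, near the levels at which treatment stops. If baloxavir affected liver tests, the cut would also differ between arms. Comparing safety between arms, including post-treatment ALT and AST elevations, is a stated objective, and these are the displays that show the course of liver tests over repeat dosing. The three descriptions of the Day 7 condition (to be dosed, planned, received) also cannot all be programmed as they stand.

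**Working it through.** The plan states no figure on this point, so the check sets the rules side by side and then illustrates size under assumptions.

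**1. Where a value goes if it barred the dose.** Assume it is the only sample in its window.

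| Sample day | Treatment under SAP 4.4 and 4.7.3 |
|---|---|
| Day 4 | Visit 4, first line of Table 2; kept |
| Day 5 | Fails the dose condition; Visit 4 missing; no other window includes Day 5 |
| Day 3 | Kept or missing, depending on whether the closing condition reaches this line; no other window |
| Day 7 | Visit 6 by Table 2; left out only if the parenthesis in 4.7.3 is applied as a filter |
| Day 8 | Fails the condition for Visit 6, but lies in the Visit 7 window, "Between Day 8 and Day 12" |
| Day 6 | As Day 3, for Visit 6 |

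A Day 8 value can therefore appear under Day 10, but only if no value nearer Day 10 exists, because 4.4 takes the nearest value for the full chemistry panel.

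**2. Which outputs carry a dose condition.** In 4.7.3 the condition sits only in the sentence on by-time-point liver statistics, changes from baseline and box plots. Table 14 counts patients over the whole study. The listing shows all laboratory data for patients with a significant change. CTC grades are given at each assessment. None of these three states a dose condition. The window text in 4.4 says that windowed values serve the analyses at each assessment time point, so the CTC-grade summary may or may not be windowed; the SAP does not say.

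**3. Does Table 14 cover the stopping criteria?** Each Appendix 4 criterion needs AST or ALT above 5×ULN, or above 3×ULN with a further finding (bilirubin, INR, or signs or symptoms). Each therefore implies AST or ALT above 3×ULN, the first row of Table 14. A grid of 132 combinations meeting an Appendix 4 criterion gave none that missed this row.

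**4. How many Day 7 values could be lost?** The documents give neither the share of patients planned for a third dose nor the share withheld for liver results. Assume 20–60% planned and 1–5% of those withheld. With 366 patients split 2:1 (244 and 122):

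- Baloxavir: 244 × 0.20 × 0.01 = 0.5, up to 244 × 0.60 × 0.05 = 7.3.
- Placebo: 122 × 0.20 × 0.01 = 0.2, up to 122 × 0.60 × 0.05 = 3.7.

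**5. What would truncation do to the display?** Assume lognormal ALT with median 1×ULN and log-SD s, and that every Day 7 value above 5×ULN is left out (the literal reading of 4.7.3). With P(>c) = 1 − Φ(ln c / s), the displayed share above 3×ULN is [P(>3) − P(>5)] / [1 − P(>5)]. The mean changes from exp(s²/2) to exp(s²/2) × Φ((ln 5 − s²)/s) / Φ(ln 5/s).

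- s = 0.6: P(>3) = 0.0335 and P(>5) = 0.0037. The share falls from 3.4% to 3.0%, the mean from 1.20 to 1.18×ULN.
- s = 1.0: P(>3) = 0.136 and P(>5) = 0.0538. The share falls from 13.6% to 8.7%, the mean from 1.65 to 1.27×ULN.

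These figures illustrate the mechanism; they do not estimate what happened in this trial.

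**The case against.** The strongest reply is that the SAP contains no explicit instruction to discard a Day 7 value. The parenthesis in 4.7.3 belongs to a clause on when samples are collected and can be read as loose shorthand for Protocol 4.5.8. Table 2 assigns an on-day sample to its visit, and the dose condition follows only the Day 5 and Day 8 lines. This stands, and it confines the explicit loss to off-day samples. It does not remove the conflict between planned and received, which a programmer must resolve one way or the other.

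The second reply is that the cases are visible elsewhere. Table 14 covers every Appendix 4 threshold. A laboratory result that changes study treatment must be reported as an adverse event (Protocol 5.3.5.4). Combined ALT or AST and bilirubin or jaundice cases are events of special interest. SAP 4.7.1 and 4.7.6 report by arm the adverse events leading to withdrawal of study drug and the missed doses, and list the reasons for the latter. This also stands. Its limit is that Table 14 stops at 5×ULN although the endpoint table extends to 10×ULN, so it does not show how far above 5×ULN a value lay, as the by-time-point displays would.

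A reader might infer that placebo patients have no Day 7 summary, because 4.7.3 names only baloxavir. The same sentence presents results by treatment group, so this is more likely loose wording than intent.

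**Conclusion.** The point holds for the by-time-point liver statistics, changes from baseline and box plots. Table 2 makes inclusion of a Day 5 sample for Visit 4 and a Day 8 sample for Visit 6, and arguably of Day 3 and Day 6 samples, depend on a dose that the sample itself may have barred. At Day 7 the exclusion follows only if the wording of 4.7.3 is applied literally as a filter.

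A reader might infer that every value above 5×ULN disappears from the liver summaries, or that a hepatic signal would be hidden. The documents do not support either. On-day values are assigned to their visit, a Day 8 value may appear under Visit 7, and the threshold counts and the listing carry no dose condition. The trial's defined liver endpoint is a set of threshold proportions, which the by-time-point displays do not determine.

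The number affected cannot be derived; the ranges above rest wholly on assumed rates and an assumed distribution. This is a free improvement to descriptive safety displays, worth making because it removes an outcome-dependent inclusion rule.

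**What to change.** Four wording changes in the SAP:

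- In 4.7.3, replace the Day 7 parenthesis with a condition that a sample was taken for a planned dose of study treatment, in either arm, whether or not the dose was then given.
- In Table 2, replace the dose condition for Visit 4 and Visit 6 with the same criterion.
- State which lines of Table 2 any remaining condition governs.
- State that Table 14 and the CTC-grade summary use all post-baseline values, including unscheduled ones.

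The cost is SAP text and the matching programming. No new data are needed, and the dosing and stopping rules stay as they are.

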4.7.4 Vital Signs

Summary statistics for all observed vital signs (diastolic blood pressures, systolic blood pressures, peripheral oxygen saturation, respiratory rate, pulse rate and body temperature) and the change from baseline to last observation on Day 10, and to patients last observation, will be presented by treatment group.

Baseline is defined as the last assessment prior to treatment.

Additionally, a graphical representation of vital signs data over time will be presented.

4.7.5 ECG

The number and proportion of patients having ECG, as well as the result (Normal, Abnormal, Abnormal, not clinically significant, Abnormal, clinically significant, Unable to evaluate), will be presented by treatment group.

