Administration of up to three doses of baloxavir marboxil separated by 3 days is planned (i.e., Days 1, 4, and 7). The dosing interval of 3 days approximates terminal disposition half-life (~ 70 hours) of baloxavir, thus higher drug exposure on Day 4 or 7 relative to the first dose is expected, under the assumption of linear pharmacokinetics. Model-based simulation indicates that the population-median accumulation in terms of maximum plasma concentration (C_{max}) and minimum *plasma* concentration (C_{trough}) prior to next dose on Day 7 (third consecutive dose) would be approximately 1.5 and 1.7 times greater than after the first dose, respectively. Based on the worst-case arithmetic mean Bayesian estimate of 126 ng/mL for C_{max} in Phase III (Asian > 80 kg), the highest peak plasma concentration after a third consecutive dose (Day 7) is not expected to exceed the peak drug levels observed in Japanese patients receiving 80 mg in the Thorough QT (TQT) study. Likewise, total drug exposure simulated on Day 7 area under the plasma concentration–time curve for a dosing interval (AUC_{tau}) is not expected to exceed area under the concentration–time curve from Time 0 to infinity (AUC_{inf}) of the TQT, regardless of dose. However, for certain individual Asian patients receiving 80 mg, total drug exposure on Day 7 (AUC_{tau}) may approach similar overall exposures as seen in the TQT.

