4.5.9 Electrocardiograms

Single ECG recordings will be obtained at specified timepoints, as outlined in the schedule of activities (see [Appendix 1](#)) and may be obtained at unscheduled timepoints.

All ECG recordings must be performed using a standard high-quality, high-fidelity digital electrocardiograph machine equipped with computer-based interval measurements. Lead placement should be as consistent as possible. ECG recordings must be performed after the patient has been resting in a supine position for at least 10 minutes. All ECGs are to be obtained prior to other procedures scheduled at that same time (e.g., vital sign measurements, blood draws) and, if possible, should not be obtained within 3 hours after any meal. Circumstances that may induce changes in heart rate, including environmental distractions (e.g., television, radio, conversation) should be avoided during the pre-ECG resting period and during ECG recording.

For safety monitoring purposes, the investigator must review, sign, and date all ECG tracings. Paper copies of ECG tracings will be kept as part of the patient's permanent study file at the site.

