5.2.1 Adverse Events

According to the ICH guideline for Good Clinical Practice, an adverse event is any untoward medical occurrence in a clinical investigation subject administered a pharmaceutical product, regardless of causal attribution. An adverse event can therefore be any of the following:

- Any unfavorable and unintended sign (including an abnormal laboratory finding), symptom, or disease temporally associated with the use of a medicinal product, whether or not considered related to the medicinal product
- Any new disease or exacerbation of an existing disease (a worsening in the character, frequency, or severity of a known condition) (see Section 5.3.5.8 and Section 5.3.5.9 for more information)
- Recurrence of an intermittent medical condition (e.g., headache) not present at baseline
- Any deterioration in a laboratory value or other clinical test (e.g., ECG, X-ray) that is associated with symptoms or leads to a change in study treatment or concomitant treatment or discontinuation from study drug
- Adverse events that are related to a protocol-mandated intervention, including those that occur prior to assignment of study treatment (e.g., screening invasive procedures such as biopsies)

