6.5 SAFETY ANALYSES

The safety analysis population will consist of all randomized patients who received at least one dose of study drug, with patients grouped according to treatment received.

All verbatim adverse event terms will be mapped to MedDRA thesaurus terms, and adverse event severity will be graded according to the NCI CTCAE v5.0 scale.

Safety will be assessed through descriptive summaries of adverse events, vital sign measurements, and laboratory test results (serum chemistry and hematology including complete blood count with differential and platelet counts).

A treatment-emergent adverse event is defined as any new adverse event reported or any worsening of an existing condition on or after the first dose of study drug.

Separate summaries will be generated for serious adverse events, deaths, adverse events leading to discontinuation of study drug, and adverse events of special interest. Adverse events will be summarized by MedDRA term, appropriate thesaurus level, and toxicity grade.

Descriptive summaries of laboratory values at baseline and throughout the study will be tabulated by treatment arm. For selected parameters, changes from baseline and the proportion of patients experiencing clinically significant changes relative to baseline will be summarized by treatment arm.

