Appendix 1 Schedule of Activities

	Treatment Period ^a											Follow-Up Period			Unsched Visit
Day(s)	D1	D2	D3	D4	D5	D6	D7	D8	D9	D10 (±2 day) ^b	Hosp Day 11+ ^c	Discharged D11–30 ^d	EOS D35 (±3 day) ^d		
Visits	Screening ^e	Random/ V1	V2	V3	V4	V5	V6			V7		V8	V9		
Administrative Procedures															
Informed consent and assent	x														
Inclusion/Exclusion criteria	x														
Baseline characteristics	x														
Medical history	x														
Concomitant medication monitoring	x		x	x	x	x	x	x	x	x	x	x	x	x	
Clinical Procedures															
Physical examination ^f	x ^f	x	x	x	x	x	x	x	x	x	x	x	x ^g	x ^g	x ^h
Body weight	x												x ^g		
Vital sign measurements ^{i, j, k}	x	x	x	x	x	x	x	x	x	x	x	x	x ^g	x ^g	x ^h
Assessment of consciousness ^{i, j, k}	x	x	x	x	x	x	x	x	x	x	x	x	x ^g	x ^g	x ^h
Presence or absence of respiratory support ^{i, j, k}	x	x	x	x	x	x	x	x	x	x	x	x	x ^g	x ^g	x ^h
Full blood hematology and chemistry ^l	x ^m										x	x ^g	x ^g	x ^g	x ^h
Blood liver chemistry ^l					x ^m				x ^m						
Electrocardiogram ⁿ	x		x												
Chest X-ray/CT Scan ^o	x	(x)													

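### SAP 4.7.5 tabulates ECG results by arm without naming the visit or comparing each patient's Day 2 ECG with the pre-dose ECG, so abnormalities present at entry are mixed with new ones

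*SAP*

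**What the plan says.** SAP 4.7.5 is a single sentence. It presents, by treatment group, "The number and proportion of patients having ECG, as well as the result". The listed results are normal, a bare abnormal, abnormal with and without clinical significance, and unable to evaluate. The sentence names no visit, defines no baseline and plans no comparison within patients. No other section of either document supplies one.

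The row "Electrocardiogram" in Protocol Appendix 1, repeated in SAP Appendix 2, is marked at screening and at Visit 2 (Day 2). Protocol 4.5.9 also allows unscheduled recordings and says that "the investigator must review, sign, and date all ECG tracings".

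The neighbouring SAP sections treat their data differently. For laboratory data (SAP 4.7.3), "Baseline is defined as the last assessment prior to treatment on Day 1", and change from baseline is summarised. Vital signs (SAP 4.7.4) also have a defined pre-treatment baseline, and the summaries include "the change from baseline to last observation on Day 10".

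Protocol 6.5 does not name ECG: "Safety will be assessed through descriptive summaries of adverse events, vital sign measurements, and laboratory test results". ECG is not among the safety endpoints in Protocol Table 1 either.

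**The concern.** An ECG that is abnormal on Day 2 may have been abnormal before the first dose. Protocol 4.1.1 lists myocarditis, pericarditis and exacerbation of ischaemic heart disease among the complications that qualify a patient for entry, and Protocol 3.3.2 sets no upper age limit. Some abnormal screening ECGs should be expected.

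A count of abnormal patients by arm combines carried-over findings with findings that arose after dosing. A safety reader wants the second group, and the planned table cannot show it. Splitting the counts by visit would help but would not be enough, because the Day 2 counts still contain the abnormalities carried over from entry. Only pairing each patient's two recordings separates them.

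What is at stake is how useful one descriptive safety table is. Efficacy, type I error and power are not touched.

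**Working it through.** The plan gives no ECG figure to reproduce. The check has a reading part and an illustration.

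**1. Are paired ECGs scheduled?** The tables were extracted from PDF, so the timing is read by column position. In both copies the ECG row has a mark in the first column (screening), a blank in the second (randomisation/Visit 1) and a mark in the third (Visit 2, Day 2). On the same column count, the study drug row falls on Visit 1, Day 4 and Day 7, which matches the dosing text. There is therefore one scheduled ECG before the first dose and one after it.

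**2. Can counts alone show new abnormalities?** Suppose n patients in an arm have both ECGs, with a0 abnormal before dosing and a1 abnormal after. The number of new abnormalities can then be anything from max(0, a1 − a0) to min(a1, n − a0). Take 366 randomised 2:1, giving 244 and 122, and assume 30% abnormal at each visit (73 of 244; 37 of 122). Even counts split by visit would fit 0 to 73 new abnormalities on baloxavir and 0 to 37 on placebo.

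**3. How much of an abnormal count could be old?** Let b be the share abnormal at entry, q the risk of a new abnormality among those normal at entry, and r the share of entry abnormalities still counted. The share of counted patients who were already abnormal at entry is

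r·b / (r·b + (1 − b)·q).

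All three inputs are assumptions. For b = 30%, q = 10%, r = 1: 0.30 / (0.30 + 0.07) = 81%.

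| b | r = 1; q = 5%, 10%, 15% | r = 0.5; q = 5%, 10%, 15% |
|---|---|---|
| 10% | 69.0, 52.6, 42.6% | 52.6, 35.7, 27.0% |
| 30% | 89.6, 81.1, 74.1% | 81.1, 68.2, 58.8% |
| 50% | 95.2, 90.9, 87.0% | 90.9, 83.3, 76.9% |
| 60% | 96.8, 93.8, 90.9% | 93.8, 88.2, 83.3% |

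The range is 43% to 97% if every entry abnormality is still counted. It is 27% to 94% if half have resolved by Day 2 and only Day 2 is counted.

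**4. What happens to the comparison of arms?** Take q = 10% v 5% with n = 244 v 122, and b and r equal in the two arms. The proportion with a new abnormality is p = (1 − b)·q. The proportion counted as abnormal is p = r·b + (1 − b)·q. The term r·b cancels, so the expected difference is (1 − b)·5 points on either measure, and there is no bias. The 95% half-width is

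1.96·√[p1(1 − p1)/244 + p2(1 − p2)/122].

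For b = 30% and r = 1, raw counts have p = 0.37 v 0.335 and a half-width of 10.3 points. New abnormalities have p = 0.07 v 0.035 and a half-width of 4.6 points.

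| b | Difference (points) | Half-width, raw counts, r = 1 | Half-width, raw counts, r = 0.5 | Half-width, new abnormalities |
|---|---|---|---|---|
| 10% | 4.5 | 8.0 | 6.8 | 5.1 |
| 30% | 3.5 | 10.3 | 8.6 | 4.6 |
| 50% | 2.5 | 10.8 | 9.8 | 3.9 |
| 60% | 2.0 | 10.5 | 10.2 | 3.5 |

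Counting new abnormalities is more precise in every row. Even so, each half-width exceeds its difference, so a doubling of risk would not be separated from zero.

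**The case against.** The strongest reply is that nothing is wrong: ECG is not a protocol endpoint, Protocol 6.5 promises no ECG summary, and the SAP already goes further than the protocol. That stands. A reader might infer a broken commitment, and the documents do not support it.

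A reader might also infer that the comparison of arms is biased. It is not, because abnormalities present at entry are balanced by randomisation in expectation.

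Nor can it be said that the planned table leaves out the screening ECG. SAP 4.7.5 does not say which visit it counts. What is missing is the pairing.

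The next reply is that adverse events already separate new from old. This is largely right. Investigators review every tracing. Protocol 5.2.1 counts as an adverse event "Any unfavorable and unintended sign (including an abnormal laboratory finding), symptom, or disease temporally associated with the use of a medicinal product", and it names ECG deterioration that brings symptoms or a change of treatment. Pre-existing conditions are reported only if they worsen (Protocol 5.3.5.8), and events are tabulated by arm (SAP 4.7.1). The remaining gap is the silent change that an investigator does not judge unfavourable enough to report.

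A shift table also has limits of its own. A patient abnormal at entry who develops a different abnormality can stay in the same category and look unchanged, and this is most likely in the cardiac patients who prompt the concern. Counts by arm identify no patient, so a listing is needed. The SAP's categories overlap and include unevaluable results, so the shift rules must say how each is handled.

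Finally, the table might be taken to cover cardiac safety under repeat dosing. It cannot, because no ECG is scheduled after the Day 4 or Day 7 dose. Protocol 3.3.1 simulates third-dose peak and trough levels that "would be approximately 1.5 and 1.7 times greater than after the first dose, respectively". It also expects the third-dose peak not to exceed levels seen in a Thorough QT study, so the protocol does address that exposure, by another route.

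**Conclusion.** The point holds as a minor, cheap improvement. SAP 4.7.5 does not name the visit or pair each patient's two scheduled ECGs, so abnormalities present at entry are mixed with those that arise after the first dose. The descriptive comparison is less informative and less precise, but not biased.

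The size depends wholly on assumed rates. With 10% to 60% abnormal at entry, all persisting, the half-width of the arm difference falls from 8.0 to 5.1 points at the low end and from 10.5 to 3.5 at the high end. These figures assume that all 366 randomised patients have both ECGs; fewer pairs would widen them.

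The gain is mainly for silent changes after the first dose. The timing of the Day 2 ECG rests on column position in the extracted schedules, on which both copies agree.

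**What to change.** In SAP 4.7.5:

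- Define ECG baseline as the last ECG before the first dose.
- Use mutually exclusive categories: normal; abnormal, not clinically significant; abnormal, clinically significant; unable to evaluate or missing.
- Show a bare abnormal result in its own row. Count it as abnormal for the normal-to-abnormal shift and leave it out of the worsening count.
- Present results by visit, and add a baseline-to-Day-2 shift table by arm. Among patients with two evaluable ECGs, give the number and proportion with a new abnormality (normal to any abnormal) or a worsening (not clinically significant to clinically significant).
- List the patients with either shift.
- Footnote that Day 2 reflects the first dose only, and that a change of abnormality type within one category is not detected.

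The cost is a few lines of SAP text, one extra descriptive table and a listing, all from results already collected. No ECGs are added, and sample size and timing are unaffected.
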